15.1 Patient Population

Due to observational nature of this study patients will not be excluded from analysis based on their performance and/or data availability. All obtained data will be summarised after procedures of data cleaning and verification. All planned analyses (including descriptive analyses and study listings) will be performed for Full Analysis Set of data.

The following patient's populations will be included into statistical analysis:

- *All Patients Enrolled population:* All patients who signed informed consent to enter the study
- *Safety population:* Patients who have taken at least one dose of any IBD medicine after enrolling in the study (Baseline visit)

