15.2.3. Analysis of Safety Data

All safety data will be analysed on the safety population. Prior to analysis, adverse drug reactions will be coded using MedDRA.

Incidence and characteristic of adverse drug reactions will be described and presented in summary tables using absolute frequencies and percentages as well as 95% confidence intervals;

Evaluation of AEs, including the AEs, will consist of the determination of total number of AEs, total number of patients with AEs and the number of AEs requiring discontinuation of the study treatment. The incidence and severity of all AEs will be summarized by body system. Treatment discontinuation due to AEs will be tabulated.

AEs reported in the study as well as AEs reported directly to authorities and to Takeda International Drug Safety according to section 11.2 and not captured in the study database will be

extracted from the overall safety database and the study database and listed or tabulated in the final report in the standard way of presenting such data in a Periodic Safety Update Report (PSUR).

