#### 8.1.5 Safety data analysis

Collection of safety data starts with the signing of ICF for this study, so, there will be no safety data available for the retrospective part of the study.

Protocol ID	MACS-2017-102279	STATISTICAL ANALYSIS PLAN	Page 27 of 41	
IP	N/A		Date	30.12.2021
ID	MACS-2017-102279_SAP		Version	v1.2 final

Safety data will be presented for the population of all patients enrolled as well as for each defined treatment combination (or pattern, if applicable) separately. Data will be presented as total counts as well as distribution by SOC at Visits 1, 2 and 3:

- Overall frequency of all AEs;
- Frequency of all AEs that led to treatment discontinuation / treatment change regardless of their relation to a particular medication;
- Frequency of SAEs;
- Frequency of all SAEs that led to treatment discontinuation / treatment change regardless of their relation to a particular medication;
- Frequency of ADRs;
- Frequency of SADRs;
- Frequency of pregnancy cases.

Additionally, all AEs/SAEs and ADRs/SADRs will be tabulated according to their relation to a particular medication (see example Table 17), separate tables will be generated for each medication being a monotherapy and in treatment combination.

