### **8.6 Analysis populations (data sets)**

Due to observational nature of this study patients will not be excluded from analysis based on their performance and/or data availability. All obtained data will be summarized after data base cleaning and lock.

All planned analyses (including descriptive analyses and study listings) will be performed for Full Analysis Set (FAS) of data.

The following patient's populations will be included into statistical analysis:

- **All Patients Enrolled population (equal to FAS):** All patients who signed informed consent to enter the study.

*Subjects that were enrolled with the violation of inclusion and subsequently withdrawn from the study (upon recognition of such violation) will be excluded from FAS and analyzed separately for baseline characteristics only (the decision whether to analyze such patients in the interim analysis will be defined by the number of such patients – summary data will be presented if this subgroup is >10 observations).*

- **Safety population:** Patients who have taken at least one dose of any IBD medicine after enrolling in the study (Baseline visit).

Due to observational nature of the study, and possible presence of missing data for analysis, it is possible to exclude several patients or the entire study center at the analysis stage.

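### The SAP presents safety on the enrolled set rather than the protocol's safety population, so adverse reactions of treated, later-withdrawn inclusion violators may drop out of the safety tables

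*SAP*

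**What the plan says.** Protocol 15.2.3 sets the rule for safety: "All safety data will be analysed on the safety population". Protocol 15.1 defines that population by a post-enrolment dose of any IBD medicine, with no eligibility condition. It defines the enrolled population as "All patients who signed informed consent to enter the study".

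SAP 8.1.5 names a different set: "Safety data will be presented for the population of all patients enrolled", with a further breakdown by treatment combination. SAP 8.6 repeats the protocol's safety population ("Patients who have taken at least one dose of any IBD medicine after enrolling in the study (Baseline visit"), but 8.1.5 does not refer to it.

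SAP 8.6 also labels the enrolled set "All Patients Enrolled population (equal to FAS". It then says that subjects enrolled in breach of the inclusion criteria and later withdrawn "will be excluded from FAS and analyzed separately for baseline characteristics only". The same section states: "All planned analyses (including descriptive analyses and study listings) will be performed for Full Analysis Set (FAS) of data". It closes by allowing some patients, or a whole centre, to be left out at the analysis stage.

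SAP section 3 presumes full agreement with the protocol, including on data sets, and asks that any difference be explained and justified. No explanation is given for this one.

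**The concern.** The safety outcomes (protocol 6.2, SAP 7.1) are the patient incidence and type of adverse drug reactions and related serious adverse events. A safety population defined by exposure counts every exposed patient, whatever is later decided about eligibility. The SAP's enrolled set does not give that protection, because a decision made after enrolment, and possibly after an event, can remove an exposed patient. It also lets patients with no post-enrolment dose into the overall denominator.

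At stake are the completeness of the event counts behind the incidence tables and the agreement between SAP and protocol on which patients those tables describe.

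**Working it through.** No figure in the plan depends on this point, so the check is a comparison of text, followed by an illustration of size.

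**1. The rules side by side**

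| Rule | Protocol | SAP |
|---|---|---|
| Set for safety | 15.2.3: safety population | 8.1.5: all enrolled, and by treatment combination or pattern |
| Safety population | 15.1: at least one post-enrolment dose | 8.6: same definition, not used in 8.1.5 |
| Enrolled set | 15.1: everyone who consented | 8.6: everyone who consented, equated with FAS, then withdrawn inclusion violators removed |
| Data of withdrawn patients | 11.5.3: enter the final analysis | 5.4.2: the same; 8.6: baseline only for withdrawn violators |
| General rule | 15.1: planned analyses on FAS | 8.6: the same |

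**2. Can an affected patient exist?** Yes. Adverse events are collected from the date after consent (protocol 13.2.3, SAP 7.2). Incorrect enrolment is a listed reason for withdrawal (protocol 11.5.1, SAP 5.4.2). Inclusion criterion 4 requires current IBD treatment, so most enrolled patients are likely to be exposed. A patient can therefore consent, take IBD medicine, have a reaction, and then be withdrawn as wrongly enrolled. Under protocol 15.2.3 that patient is counted. Under the FAS of SAP 8.6, only the baseline data are.

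**3. Illustration of size.** The planned enrolment of about 2000 comes from protocol section 11. Everything else is an assumption, because the documents give no rates:

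- v = share of withdrawn inclusion violators, 1–5%, all of them dosed
- u = share of the remaining patients with no post-enrolment dose, 0–5%
- r = reaction risk in dosed non-violators, 5%
- r_v = reaction risk in violators, 5–20%

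Patients removed: 2000 × v = 20 to 100.

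Patients with a reaction removed: 2000 × v × r_v, from 20 × 0.05 = 1 to 100 × 0.20 = 20.

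Incidence on the SAP set (if violators are excluded) = r(1 − u).

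Incidence on the safety population = [r(1 − v)(1 − u) + r_v·v] / [(1 − v)(1 − u) + v].

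| v | u | r_v | SAP set | Safety population |
|---|---|---|---|---|
| 1% | 0 | 5% | 99/1980 = 5.00% | 100/2000 = 5.00% |
| 3% | 2% | 10% | 95.06/1940 = 4.90% | 101.06/1961.2 = 5.15% |
| 5% | 0 | 20% | 95/1900 = 5.00% | 115/2000 = 5.75% |
| 5% | 5% | 5% | 90.25/1900 = 4.75% | 95.25/1905 = 5.00% |
| 5% | 5% | 20% | 90.25/1900 = 4.75% | 110.25/1905 = 5.79% |

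The third row isolates the removal of violators: at most 0.75 percentage points on these assumptions, and nothing if their risk equals that of other patients. The fourth row isolates dilution by undosed patients: 0.25 points if as many as 5% take no dose. Where violators have ordinary risk, the loss is in event counts rather than in the percentage.

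**The case against.** Several points on the other side stand.

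- **The protocol is not of one mind.** Its section 15.1 also puts all planned analyses on the Full Analysis Set, and SAP 8.6 copies that sentence. A reader might infer that the SAP breaks an unambiguous protocol rule; it does not. Still, 15.2.3 is the sentence specific to safety, and the protocol's enrolled set has no exclusion for violators. Neither protocol sentence supports dropping treated violators.
- **Exclusion is the likely reading, not the only one.** A reader might infer that these patients' reactions certainly leave the safety tables. SAP 8.1.5 says all enrolled rather than FAS, the definition in 8.6 begins with everyone who consented, and SAP 5.4.2 keeps withdrawn patients' data in the final analysis. SAP 8.1.5 also promises tabulation of all events by related medication. Against that, 8.6 expressly equates the enrolled set with the FAS and restricts withdrawn violators to baseline data. The text conflicts with itself, so the right word is may.
- **The events are not lost to all reporting.** Protocol 15.2.3 foresees listing or tabulation of adverse events from the study and overall safety databases in PSUR style. SAE reporting under protocol 13.2.4 and 13.2.5 does not depend on analysis sets. Neither repairs the incidence tables that answer the safety outcomes.
- **The group is narrow.** A patient must breach an inclusion criterion and also be withdrawn for it. Violators who stay in the study remain in the FAS.
- **Dilution is minor.** Criterion 4 makes an undosed patient unusual, and the tables by treatment combination are defined by the treatment used.

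**Conclusion.** The point holds as a correction to the SAP. SAP 8.1.5 and protocol 15.2.3 name different sets for safety, the SAP defines the right set without using it in any analysis section available here (the table shells of SAP section 9 were not), and the required rationale is absent. Because of the FAS exclusion in SAP 8.6, reactions in treated, later-withdrawn inclusion violators may be missing from the SAP incidence tables and FAS listings. That conflicts with protocol 11.5.3 and SAP 5.4.2.

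The effect is probably small: 1 to 20 patients with a reaction under the assumptions shown, none of which comes from the documents. The study is descriptive and no hypothesis test is affected. The option in SAP 8.6 to leave out patients or a centre could widen the loss in the same way, because nothing exempts the safety population from it.

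**What to change.** 1. **SAP 8.1.5:** name the safety population as the set for all safety tables and listings, overall and by treatment combination or pattern.
2. **SAP 8.6:** state that neither the FAS exclusion of withdrawn inclusion violators nor the option to leave out patients or a centre applies to the safety population. A patient with a post-enrolment dose stays in it whatever the later eligibility decision.
3. **Protocol 15.1 and SAP 8.6:** qualify the sentence that puts all planned analyses on the FAS, so that it excepts safety in line with protocol 15.2.3.

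If the sponsor prefers the enrolled set, the alternative is to give the rationale that SAP section 3 requires and to say explicitly where the withdrawn violators' events will be shown.

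The cost is a sentence or two in each section. No new data and no change to patient care are needed. Safety tables already produced would have to be rerun, with the change recorded in the study report as SAP 8.5 provides.

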Existing treatment methods show insufficient effectiveness. Aminosalicylates are only modestly effective; glucocorticoids can cause unacceptable adverse events and do not provide a benefit as maintenance therapy. Tumor necrosis factor (TNF) antagonists, although efficacious, may predispose patients to infections and other serious adverse reactions [3, 4, 6-10, 12, 28, 29]. Besides, a considerable portion of patients do not respond to the treatment with TNF-antagonists (primary non-responders) or will lose response to such therapies over time (secondary loss of response). New biological treatment medication Vedolizumab (Entyvio®) is the first and only gut selective biologic approved medication indicated for the treatment of adult patients with moderate to severe UC and CD, who have had an inadequate response with, lost response to, or were intolerant to either non-biological therapy or a tumor necrosis factor-alpha (TNF α) antagonists [15, 16, 25, 26].

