# 7 SAFETY AND EXPLORATORY ASSESSMENTS

## 7.1 ***Safety endpoints (outcomes):***

- Patient incidence and type of adverse drug reactions related to IBD treatment occurring during 12-months treatment period within routine clinical practice by treatment type (biologics or non-biological therapy) and treatment history (biologic treatment naïve or with prior biological treatment);
- Patient incidence and type of serious adverse events related to IBD treatment occurring during 12-months treatment period within routine clinical practice by treatment type (biologics or non-biological therapy) and treatment history (biologic treatment naïve or with prior biological treatment).

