## 8 STATISTICAL DATA PROCESSING

### 8.1 Statistical methods

#### 8.1.1 General information

Statistical analysis will be conducted using the software package Microsoft R Open version 4.0.2 from Microsoft R Application Network (MRAN) (<https://mran.microsoft.com>). Exact version of the software will be determined at the time of first interim analysis and will remain unchanged throughout the study. Version control for the software and related R packages used for statistical data processing will be performed using the CRAN Time Machine from Microsoft (or the purpose of reproducibility, MRAN hosts daily snapshots of the CRAN R packages and R releases as far back as Sept. 17, 2014). Statistical analysis will take data type and scale for each parameter when describing and analyzing the data.

Quantitative data (both continuous and discrete, if applicable) will be presented using the following parameters:

- Number of non-missing observations (n);
- Arithmetic mean (M);
- Standard deviation (SD);
- 95% confidence interval for the mean (95% CI);
- Median (Me);
- 25th percentile;
- 75th percentile;
- Minimal value (min);
- Maximal value (max);

Qualitative data including binary and categorical variables will be presented as number of cases per category, frequency for the category (relative to the non-missing number of observations), as well as 95% exact binary confidence interval calculated using Clopper-Pearson method (binary data) or Goodman method (categorical data).

Time-to-event data will be presented as median, 25th and 75th percentiles as well as graphically as Kaplan-Meyer survival curves with log-log 95% confidence intervals.

No statistical tests are planned for the primary endpoint of this study as all outputs will be purely descriptive. However, 95% significance level will be applied for all confidence intervals calculated, and exploratory statistical analysis will be conducted to identify statistically significant associations between treatment patterns and outcomes.

Medical history, concomitant conditions and adverse events will be coded using the MedDRA dictionary. As version of MedDRA is updated every six months, the first interim analysis will be conducted using the most current MedDRA version, and all subsequent analyses, including the

Protocol ID	MACS-2017-102279	STATISTICAL ANALYSIS PLAN	Page 23 of 41	
IP	N/A		Date	30.12.2021
ID	MACS-2017-102279_SAP		Version	v1.2 final

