**The same information will be provided for the treatment pattern (if the corresponding treatment pattern will be large enough to make statistical inferences).**

As treatment pattern change over time, patterns will be assessed for certain time points and the change of patterns will be tracked throughout the study (see also example Table 8):

- Retrospective treatment pattern (change assessment for every 6 months of the 2-year treatment interval);
- Treatment pattern between the date of enrollment and 6 months;
- Treatment pattern between 6 and 12 months.

Accordingly, for each above-mentioned period, each pattern will be assessed for the history of changes (see example Table 8):

- Presence of dose modifications;
- Presence of discontinuations / treatment changes;
- Presence of flares (during the course of treatment);
- Add-on therapy.

Protocol ID	MACS-2017-102279	STATISTICAL ANALYSIS PLAN	Page 26 of 41	
IP	N/A		Date	30.12.2021
ID	MACS-2017-102279_SAP		Version	v1.2 final

In order to track the history of transition of subject “states” (i.e. treatment using the certain pattern from the list above), in addition to the descriptive 6-monthly data, transition state (Sankey) diagrams will be built (see Figure 2 for mock example) to visualize the subject journey across patterns as well as trends of pattern change over time.

Treat-to-target (T2T) success will be assessed (in this SAP) using EDC data, based on the definition of failure to meet T2T goals (*lack of clinical and endoscopic remission based on investigator's feedback and objective methods of evaluation*). Overall T2T success or failure will be analyzed separately from this SAP using Investigator Survey data.

T2T treatment factors will be assessed by Visits 1, 2 and 3 and will be grouped by:

- Clinician-related factors:
  - Frequency and methods of assessment of UC/CD disease activity;
- Patient-related factors:
  - Demographic data;
  - Time frame between the date of first symptom(s) and the date of IBD diagnosis;
  - Smoking status;
- Disease-related factors:
  - Age of disease onset;
  - Location of disease;
  - Clinical course;
  - Disease severity;
  - Presence of intestinal and systemic (extraintestinal) manifestations;
  - Presence of complications;
  - Surgical treatment.

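### Safety is tabulated per treatment combination as counts and frequencies, with no exposure denominator and no stated rule for which combination an event belongs to

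*SAP*

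**What the plan says.** The safety endpoints in SAP 7.1 are the patient incidence and type of ADRs, and of SAEs related to IBD treatment, "occurring during 12-months treatment period within routine clinical practice by treatment type (biologics or non-biological therapy"), and by whether the patient is biologic-naive or has had a biologic before.

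SAP 8.1.5 sets the presentation: all enrolled patients, "as well as for each defined treatment combination (or pattern, if applicable) separately". On the measure it says: "Data will be presented as total counts as well as distribution by SOC at Visits 1, 2 and 3". SAP 8.1.1 defines a category's share as "frequency for the category (relative to the non-missing number of observations"). Protocol 15.2.3 is similar for ADRs, which are to be "presented in summary tables using absolute frequencies and percentages as well as 95% confidence intervals". Neither text gives a rate per patient-time, an on-treatment window or a time-to-first-ADR analysis for safety. Kaplan-Meier is named in general terms (Protocol 15.2.2, SAP 8.1.1) but is not assigned to a safety outcome.

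One dose is enough for the safety population: "Patients who have taken at least one dose of any IBD medicine after enrolling in the study" (SAP 8.6). Therapy is expected to move: "As treatment pattern change over time, patterns will be assessed for certain time points" (SAP 8.1.3). Steroid monotherapy is one of the listed combinations (SAP 8.1.2), and Protocol 5.1 says that glucocorticoids "do not provide a benefit as maintenance therapy".

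**The concern.** Twelve months is the planned length of observation, not the time on any one therapy. A percentage of patients with an event depends on both the underlying rate and the time at risk. When columns with different time at risk stand side by side, a reader cannot separate the two.

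The safety objective is to describe incidence by treatment type. Without an attribution rule and an exposure denominator, the tables cannot say clearly whose incidence is being described, or over what time.

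**Working it through.** **Figures in the documents.** There is no planned ADR rate, expected course length or safety precision figure to reproduce. The only design calculation concerns treatment failure: n = 2000 × 0.4 × 0.4 × 0.9 = 288 and 1.96 × √(0.5 × 0.5/288) = 5.8%, as Protocol 15.4 states. It does not bear on safety. All rates and durations below are therefore assumptions.

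**Reading A: events counted while on the combination.** The tables by related medication in SAP 8.1.5, split into monotherapy and combination, point this way. With a constant rate r per patient-year and m months of exposure, the expected share with at least one ADR is 1 − exp(−r × m/12).

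| First ADRs per 100 patient-years (assumed) | 3 months | 6 months | 12 months | Ratio 12 v 3 |
|---|---|---|---|---|
| 10 | 2.5% | 4.9% | 9.5% | 3.85 |
| 20 | 4.9% | 9.5% | 18.1% | 3.72 |
| 30 | 7.2% | 13.9% | 25.9% | 3.59 |
| 50 | 11.8% | 22.1% | 39.3% | 3.35 |
| 100 | 22.1% | 39.3% | 63.2% | 2.86 |

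The true rate is the same in every column of a row, so the gap comes from exposure alone. If the visit tables are read as separate half-year intervals, exposure per table is at most about 6 months. At 20 per 100 patient-years the comparison is then 9.5% v 4.9%, a ratio of 1.95.

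**The same data as rates.** Take 100 patients per column at 20 per 100 patient-years, with time censored at the first event.
- 3 months: 4.88 patients with an event over 4.88/0.20 = 24.4 patient-years, which is 20 per 100.
- 12 months: 18.13 over 18.13/0.20 = 90.6 patient-years, which is 20 per 100.

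The ratio of rates is 1.0.

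**When the hazard is not constant.** Suppose the rate of 20 applies only in the first 3 months of a course and is zero afterwards. Both columns then show 4.9%, so the percentage gap vanishes. The 12-month column accrues 24.4 + 95.1 × 0.75 = 95.7 patient-years, so its rate is 4.88/95.7 = 5.1 per 100 against 20 in the 3-month column. Here the rate misleads in the opposite direction, which is why both measures should be shown. If an ADR itself ends the course, a poorly tolerated combination has short exposure and a high percentage, and the direction can reverse.

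**Reading B: columns by original combination.** SAP 8.1.3 defines this as the first combination recorded at the start of the retrospective period, two years before consent. Safety data start at consent. Follow-up is then about 12 months in each column, apart from early withdrawals, and the exposure artefact largely goes. But an event at Month 12 would be credited to a combination recorded up to 24 + 12 = 36 months earlier, which may have been stopped long before.

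**Reading C: columns by pattern.** A pattern includes its own changes over time (SAP 8.1.2). Follow-up is again about equal, but the column does not say which therapy was in use when the event occurred.

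**The case against.** The strongest reply is that the exposure artefact depends on Reading A, which the SAP does not state. That stands: under B or C follow-up is about equal. It does not clear the plan, because B and C replace the artefact with uncertain attribution and 8.1.5 does not choose between the readings.

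Four further points have weight.
- The tables are descriptive, and SAP 8.3 plans no tests on them. It would be too strong to say that the plan formally compares combinations on safety. SAP 8.1.1 does plan an exploratory search for associations between patterns and outcomes, but it does not name safety outcomes.
- The endpoint in SAP 7.1 is by two treatment types and by biologic history. The documents do not show that exposure differs much between those groups.
- Duration of use is already summarised (SAP 8.1.2). However, the total pools retrospective and prospective time and is not linked to the safety tables.
- The example table cited in SAP 8.1.5 (Table 17) was not in the text available to me, so I cannot exclude a person-time column there.

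A reader might infer that short steroid courses will always look safer than year-long therapy, or that a 3.7-fold distortion is to be expected. The documents support neither. They give no steroid course length, the direction depends on how ADRs fall within a course, and the factor comes from assumed inputs.

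**Conclusion.** The point holds as a gap in specification. The plan's text gives safety by combination as counts and frequencies, without an exposure denominator and without a rule that ties an event to a combination. If events are counted on treatment, the rate is constant and courses last 3 and 12 months (all assumed), the crude percentages differ by a factor of 2.9 to 3.9 with no true difference. With half-year tables and a rate of 20 the factor is about 2. With early clustering it can fall to 1, and with ADR-driven stopping it can reverse. That exposure differs between combinations is inferred from treatment changes and the one-dose entry rule; the documents do not quantify it. The remedy is cheap and should be adopted.

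**What to change.** In SAP 8.1.5:

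1. Assign each event to the combination in use at onset. Add a stated lag window after stopping, because the causality definition in Protocol 13.1.5 covers the course after a drug is withdrawn.
2. Derive post-consent patient-years on each combination from the recorded treatment dates (Protocol 12.6.1), with a written rule for incomplete dates. Event onset dates and the medication concerned are already on the AE form (Protocol 13.2.2).
3. Beside n (%), report the rate of first ADR and of first related SAE per 100 patient-years, with time censored at the first event and exact Poisson 95% CIs. If recurrent events are counted, use intervals that allow for clustering within patient.
4. Do the same for the endpoint groups: biologic v non-biological, and biologic-naive v prior biologic.
5. Base any reading across columns on ADR and SAE rates, not on all-AE rates. Under Protocol 13.2.3, non-serious AEs regardless of causality are collected only for vedolizumab, and person-time cannot repair that.

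No new data are needed, and n (%) stays, so Protocol 15.2.3 is still met. The cost is some programming and the partial-date rule. Rates in small columns will be imprecise: 25 patients (the limit in SAP 8.1.2 below which a combination may be dropped) with 3 months each give at most 6.25 patient-years and about 1.2 expected first ADRs at the assumed rate of 20. Record the change under SAP 8.5. If data collection has already ended, Protocol 15 requires it to be summarised in the study report.
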